5.3 Exclusion criteria

Patients eligible for this study must **not** meet **any** of the following criteria:

1. Patient with symptomatic visceral disease or any disease burden that makes the patient ineligible for endocrine therapy per the investigator's best judgment.
2. Patient who received any prior CDK4/6 inhibitor
3. Patient who received any prior mTOR-inhibitor
4. Patient has a known hypersensitivity to any of the excipients of ribociclib, letrozole (or goserelin if pre- or perimenopausal)
5. Patients with current inflammatory breast cancer (< 4 weeks before enrollment).
6. **For Cohort A:** prior treatment for advanced or metastatic disease
 - Patients who received \leq 21 days of aromatase inhibitor treatment for advanced disease prior to enrollment are eligible.

Note: Patients starting study treatment directly after any endocrine anti-cancer therapy within less than 5 half-lives of the previous therapy should be monitored closely for possible overlapping toxicities.

7. **For Cohort B:**

- Patient who has received more than one prior chemotherapy regimen for advanced breast cancer
AND/OR
- Patient who has received more than two prior hormonal therapy regimens for advanced breast cancer. (Treatment for \leq 21 days with an aromatase inhibitor for advanced disease is not considered an endocrine therapy line).

8. Patient is concurrently using other anti-cancer therapy. (Treatment with bisphosphonates or denosumab is generally not considered anti-cancer therapy).
9. Patient has had major surgery within 14 days prior to starting study drug or has not recovered from major side effects.
10. Patient has not recovered from all toxicities related to prior anticancer therapies to NCI CTCAE version 4.03 Grade \leq 1. Exception to this criterion: patients with any grade of alopecia are allowed to enter the study.
11. Patient has a concurrent malignancy or malignancy within 3 years of enrollment, with the exception of adequately treated, basal or squamous cell skin carcinoma, non-melanomatous skin cancer or curatively resected cervical cancer.
12. Patients with central nervous system (CNS) involvement unless they meet ALL of the following criteria:
 - At least 4 weeks from prior therapy completion (including radiation and/or surgery) to starting the study treatment.
 - Clinically stable CNS tumor at the time of screening and not receiving steroids and/or enzyme inducing anti-epileptic medications for brain metastases.
13. Patient has impairment of gastrointestinal (GI) function or GI disease that may significantly alter the absorption of the study drugs (e.g., ulcerative diseases, uncontrolled nausea, vomiting, diarrhea, malabsorption syndrome, or small bowel resection)
14. Patient has a known history of HIV infection (testing not mandatory).
15. Patient has any other concurrent severe and/or uncontrolled medical condition that would, in the investigator's judgment, cause unacceptable safety risks,

contraindicate patient participation in the clinical study or compromise compliance with the protocol: (e.g. chronic pancreatitis, chronic active hepatitis, active untreated or uncontrolled fungal, bacterial or viral infections, etc.).

16. Clinically significant, uncontrolled heart disease and/or cardiac repolarization abnormality, including any of the following:
 - History of acute coronary syndromes (including myocardial infarction, unstable angina, coronary artery bypass grafting, coronary angioplasty, or stenting) or symptomatic pericarditis within 6 months prior to screening.
 - History of documented congestive heart failure (New York Heart Association functional classification III-IV).
 - Documented cardiomyopathy.
 - Clinically significant cardiac arrhythmias (e.g. ventricular tachycardia), complete left bundle branch block, high-grade AV block (e.g. bifascicular block, Mobitz type II and third-degree AV block).
 - Long QT syndrome or family history of idiopathic sudden death or congenital long QT syndrome, or any of the following:
 - Risk factors for Torsades de Pointe (TdP) including uncorrected hypokalemia or hypomagnesemia, history of cardiac failure, or history of clinically significant/symptomatic bradycardia.
 - Concomitant use of medication(s) with a known risk to prolong the QT interval and/or known to cause Torsades de Pointe that cannot be discontinued (within 5 half-lives or 7 days prior to starting study drug) or replaced by safe alternative medication.
 - Inability to determine the QT interval on screening (QTcF, using Fridericia's correction).
 - Systolic blood pressure (SBP) >160 mmHg or <90 mmHg at screening.
17. Patient is currently receiving any of the following substances and cannot be discontinued 7 days prior to Cycle 1 Day 1:
 - Known strong inducers or inhibitors of CYP3A4/5, including grapefruit, grapefruit hybrids, pomelos, star-fruit, and Seville oranges.
 - That have a narrow therapeutic window and are predominantly metabolized through CYP3A4/5.
 - Herbal preparations/medications. Dietary supplements are allowed if they contain only nutrients, minerals and/or vitamins.
18. Patient is currently receiving or has received systemic corticosteroids \leq 2 weeks prior to starting study drug, or who have not fully recovered from side effects of such treatment.
Note: The following uses of corticosteroids are permitted: single doses, topical applications (e.g., for rash), inhaled sprays (e.g., for obstructive airways diseases), eye drops or local injections (e.g., intra-articular).
19. Participation in a prior investigational study within 30 days prior to enrollment or within 5-half-lives of the investigational product, whichever is longer.
20. For premenopausal women: Pregnant or nursing (lactating) women, where pregnancy is defined as the state of a female after conception and until the termination of gestation, confirmed by a positive hCG laboratory test.
21. Women of child-bearing potential, defined as all women physiologically capable of becoming pregnant, **unless** they are using highly effective methods of contraception during dosing of study treatment. Highly effective contraception methods include:

- Total abstinence (when this is in line with the preferred and usual lifestyle of the subject. Periodic abstinence (e.g., calendar, ovulation, symptothermal, post-ovulation methods) and withdrawal are not acceptable methods of contraception
- Female sterilization (have had surgical bilateral oophorectomy with or without hysterectomy) or tubal ligation at least six weeks before taking study treatment. In case of oophorectomy alone, only when the reproductive status of the woman has been confirmed by follow up hormone level assessment
- Male sterilization (at least 6 months prior to screening). For female subjects on the study the vasectomized male partner should be the sole partner for that subject.
- Combination of:
 - Placement of an intrauterine device (IUD) or intrauterine system (IUS)
 - Barrier methods of contraception: Condom or Occlusive cap (diaphragm or cervical/vault caps) with spermicidal foam/gel/film/cream/vaginal suppository

Note: sexually active males should use a condom during intercourse while taking drug and for 21 days after stopping medication and should not father a child in this period. A condom is required to be used also by vasectomized men as well as during intercourse with a male partner in order to prevent delivery of the drug via seminal fluid.

6 Treatment

6.1 Study treatment

For this study, the term “investigational drug” refers to Novartis study drug ribociclib (LEE011). The other investigational drugs to be used in this study are letrozole as well as goserelin acetate for pre-and perimenopausal women; men may also be treated with goserelin acetate at the discretion of the investigator. Study treatment in this study refers to the combination of drugs and includes investigational drug (ribociclib) as well as letrozole and goserelin acetate.

Novartis will provide ribociclib and letrozole (and goserelin) for all patients who are enrolled prior to commercial availability of ribociclib. For patients enrolled afterwards within the approved indication according to SmPC, the investigator will prescribe both ribociclib and letrozole after evaluation of the individual medical patient need for the treatment with ribociclib and letrozole. Patients who are enrolled outside of the label according to SmPC will be provided with study drug by Novartis (i.e. patients in cohort B).

Patients enrolled after commercial availability of ribociclib and letrozole, who are to be treated within the label and are covered by private health insurance should contact their private health insurance to ensure that the insurance will cover the costs of the prescription.

Ribociclib will be supplied by Novartis or its designee as 200 mg film-coated tablets as individual patient supply packaged in bottles or blisters. Letrozole and goserelin acetate will be procured locally as it is commercially available in Germany. Storage conditions are described in the medication label.

All dosages prescribed and dispensed to the patient and all dose changes during the study must be recorded on the Dosage Administration Record eCRF. On the first day of each cycle, patients will receive an adequate drug supply (before commercial availability) or a prescription (after commercial availability) for self-administration at home.

The investigator must emphasize compliance and will instruct the patient to take ribociclib (LEE011) and letrozole as well as goserelin exactly as prescribed.

6.1.1 Dosing regimen

Table 6-1 Dose and treatment schedule

Study treatments	Pharmaceutical form and route of administration	Dose	Frequency and/or Regimen
Ribociclib	Tablet for oral use	600 mg (3x200mg)	Once daily - Days 1-21 of each 28 day cycle
Letrozole	Tablet for oral use	2.5 mg	Once daily
Goserelin (for premenopausal patients)	Subcutaneous implant	3.6mg	Day 1 of each cycle

Ribociclib will be given orally once a day on days 1-21 of each 28 day cycle. Days 22-28 will be a “rest” from ribociclib. Letrozole will be given every day. Goserelin will be injected monthly for pre- or perimenopausal patients only.

Ribociclib, letrozole and goserelin will be administered as a flat-fixed dose, and not by body weight or body surface area.

The investigator or responsible site personnel should instruct the patient to take the study drugs as per protocol (promote compliance). Drug accountability must be performed on a regular basis. Patients will be instructed to return unused study drugs to the site at the end of each cycle. The site personnel will ensure that the appropriate dose of each study drug is provided at each visit.

6.1.1.1 Ribociclib dosing

Ribociclib should be taken as follows:

- Ribociclib is dosed for the first 21 days out of the 28 day cycle.
- Patients should be instructed to take the study drug combination of ribociclib and letrozole with a large glass of water (~250 mL) at the same time each day. Evening doses are strongly not recommended.
- Ribociclib can be administered with or without food; however dietary habits around the time of dosing should be as consistent as possible throughout the study.
- Patients should be instructed to swallow the ribociclib whole and not to chew or crush them.
- If vomiting occurs during the course of treatment, no re-dosing of the patient is allowed before the next scheduled dose. The occurrence and frequency of any vomiting during a treatment cycle must be noted in the adverse events section of the eCRF.
- Any doses that are missed (not taken within 6 hours of the intended time) should be skipped and should not be replaced or made up on a subsequent day.

- Patients must avoid consumption of grapefruit, grapefruit hybrids, pomelos, starfruit, Seville oranges or products containing the juice of each during the entire study and preferably 7 days before the first dose of study medications, due to potential CYP3A4 interaction with the study medications.

Note: Orange juice is allowed.

1. Herbal or dietary supplements known as strong inhibitors or inducers of CYP3A4 or those with a known risk of QT prolongation are not permitted.
2. Multivitamins are permitted.

6.1.1.2 Additional dosing guidelines for ECG/Chemistry panel/Lipid Panel collection

On days with ECG sampling, chemistry panel and/or lipid panel sampling, the following additional guidelines should be followed:

- On a day of chemistry panel, hepatic safety markers and/or lipid panel sampling, patients must be fasting from all food and drink for at least 8 hours overnight. Water is allowed during all fasting periods; however coffee, tea and juice are not permitted during the fasting period. Patients must also take study treatment in the clinic under the supervision of the Investigator or designee. On all other days patients may take the study treatment at home.
- If a pre-dose ECG measurement should be collected, then the ECG measurement should occur before dosing of the study treatment

6.1.2 Treatment duration

Patient may continue treatment with the study drug until patient experiences unacceptable toxicity, disease progression (any radiologic according to RECIST 1.1) and/or treatment is discontinued at the discretion of the investigator or withdrawal of consent must be documented accordingly.

Study drug interruption refers to a patient stopping either study drug during the course of the study, but then re-starting it at a later time in the study. If one of the study drugs is discontinued, the other must be discontinued as well. If the study drug ribociclib or letrozol is interrupted for more than 4 weeks, the patient will be permanently discontinued from the study treatment.

6.2 Dose modifications

6.2.1 Dose modification and dose delay

For patients who do not tolerate the protocol-specified dosing schedule, dose adjustments are permitted in order to allow the patient to continue the study treatment. The following guidelines need to be applied:

Table 6-2 Dose Modification guidelines

	Ribociclib	
	Dose	Number of tablets & strength
Starting dose	600 mg	3 x 200 mg tablets
First dose reduction	400 mg	2 x 200 mg tablets
Second dose reduction	200 mg	1 x 200 mg tablets

These changes must be recorded on the Dosage Administration Record CRF.

6.2.1.1 Ribociclib

Recommendations for dose reduction, interruption or discontinuation of ribociclib in the management of study drug related adverse reactions are summarized in [Table 6-3](#), [Table 6-4](#), [Table 6-5](#) and [Table 6-6](#).

Clinical judgment of the treating physician should guide the management plan of each patient based on individual benefit/risk assessment. However, for events requiring a discontinuation in [Table 6-3](#), [Table 6-4](#), [Table 6-5](#) and [Table 6-6](#) or listed in Section 7.1, treatment must be discontinued.

If a patient inadvertently doses ribociclib on a rest day (e.g. days 22-28 of any given cycle), ribociclib should be interrupted to ensure 7 consecutive rest days and avoid overdose. The visit schedule will not be adjusted.

Table 6-3 Ribociclib dose adjustment and management recommendations for hematological adverse reactions

Toxicity/Grade	Dose Adjustment and Management Recommendations
Thrombocytopenia	
Grade 1($\geq 75 \times 10^9/L$)	No dose adjustment required.
Grade 2 ($\geq 50 \times 10^9/L - < 75 \times 10^9/L$)	Dose interruption until recovery to grade ≤ 1 . Re-initiate ribociclib at the same dose.
Grade 3 ($\geq 25 \times 10^9/L - < 50 \times 10^9/L$)	Dose interruption until recovery to grade ≤ 1 . Re-initiate ribociclib at the same dose level. If toxicity recurs at grade 3: temporary dose interruption until recovery to grade ≤ 1 and reduce ribociclib to the next lower dose level.
Grade 4($< 25 \times 10^9/L$)	Dose interruption until recovery to grade ≤ 1 . Re-initiate ribociclib at the next lower dose level. If toxicity recurs at grade 4: discontinue ribociclib
Absolute neutrophil count (ANC),	
Grade 1 ($\geq 1.5 \times 10^9/L$)	No dose adjustment required.
Grade 2 ($\geq 1.0 - < 1.5 \times 10^9/L$)	No dose adjustment required.

Toxicity/Grade	Dose Adjustment and Management Recommendations
Grade 3 ($\geq 0.5 - < 1.0 \times 10^9/L$)	
Dose interruption until recovery to $\geq 1.0 \times 10^9/L$. Re-initiate ribociclib at the same dose level. If toxicity recurs at grade 3: temporary dose interruption until recovery to $\geq 1.0 \times 10^9/L$. If resolved in ≤ 7 days, then maintain dose level. If resolved in > 7 days, then reduce ribociclib dose to the next lower dose level.
 
For Grade 3 neutropenia without fever or signs of infection on Day 14 of the first 2 cycles: Consider to continue ribociclib at current dose level to complete cycle. Repeat complete blood count on Day 21. Consider dose reduction based on the neutropenia recovery (<7 days / > 7 days).

Grade 4 ($< 0.5 \times 10^9/L$)	
Dose interruption until recovery to $\geq 1.0 \times 10^9/L$. Re-initiate ribociclib at the next lower dose level. If toxicity recurs at grade 4: temporary dose interruption until recovery to $\geq 1.0 \times 10^9/L$ and reduce ribociclib at the next lower dose level.

Leukocyte count (WBC)	
Grade 1 ($< LLN - 3.0 \times 10^9/L$)	No dose adjustment required.
Grade 2 ($< 3.0 - 2.0 \times 10^9/L$)	No dose adjustment required.
Grade 3 ($< 2.0 - 1.0 \times 10^9/L$)	
Dose interruption until recovery to $\geq 2.0 \times 10^9/L$. Re-initiate ribociclib at the same dose level. If toxicity recurs at grade 3: temporary dose interruption until recovery to $\geq 1.0 \times 10^9/L$. If resolved in ≤ 7 days, then maintain dose level. If resolved in > 7 days, then reduce ribociclib dose to the next lower dose level.

Grade 4 ($< 1.0 \times 10^9/L$)	
Dose interruption until recovery to $\geq 1.0 \times 10^9/L$. Re-initiate ribociclib at the next lower dose level. If toxicity recurs at grade 4: temporary dose interruption until recovery to $\geq 1.0 \times 10^9/L$ and reduce ribociclib at the next lower dose level.

Febrile neutropenia	
Grade 3 ANC $< 1.0 \times 10^9/L$ with a single temperature of $> 38.3^\circ C$ ($101^\circ F$) or a sustained temperature of $\geq 38^\circ C$ ($100.4^\circ F$) for more than one hour	
Dose interruption until improvement of ANC $\geq 1.0 \times 10^9/L$ and no fever. Restart at the next lower dose level. If febrile neutropenia recurs, discontinue ribociclib.

Grade 4 Life-threatening consequences; urgent intervention indicated	Discontinue ribociclib.
Anemia (Hemoglobin)	
Grade 1 ($\geq 10.0 - LLN$ g/dL)	No dose adjustment required.
Grade 2 ($\geq 8.0 - < 10.0$ g/dL)	No dose adjustment required.
Grade 3 (< 8.0 g/dL)	Dose interruption until recovery to grade ≤ 2 . Re-initiate ribociclib at the same dose.
Grade 4 Life-threatening consequences; urgent intervention indicated	Discontinue ribociclib.

Table 6-4 **Ribociclib dose adjustment and management recommendation for hepatic toxicities**

HEPATOTOXICITY (BILIRUBIN, SGPT/ALT, SGOT/AST)	
TOTAL BILIRUBIN without ALT/AST increase above baseline value	
Grade 1 (> ULN – 1.5 x ULN) (confirmed 48-72h later)	Maintain dose level with LFTs monitored bi-weekly
Grade 2 (> 1.5 – 3.0 x ULN)	
Dose interruption of ribociclib
 
If resolved to ≤ grade 1 in ≤ 21 days, then maintain dose level
 
If resolved to ≤ grade 1 in > 21 days or toxicity recurs, then reduce 1 dose level
 
Repeat liver enzyme and bilirubin tests twice weekly for 2 weeks after dose resumption
 
If toxicity recurs after two dose reductions, discontinue ribociclib

Grade 3 (> 3.0 – 10.0 x ULN)	
Dose interruption of ribociclib
 
If resolved to ≤ grade 1 in ≤ 21 days, lower 1 dose level of ribociclib
 
Repeat liver enzyme and bilirubin tests twice weekly for 2 weeks after dose resumption
 
If resolved to ≤ grade 1 in > 21 days or toxicity recurs, discontinue ribociclib

Grade 4 (> 10.0 x ULN)	Discontinue ribociclib
Confounding factors and/or alternative causes for increase of total bilirubin should be excluded before dose interruption/reduction. They include but are not limited to: evidence of obstruction, such as elevated ALP and GGT typical of gall bladder or bile duct disease, hyperbilirubinemia due to the indirect component only (i.e. direct bilirubin component ≤ 1 x ULN) due to hemolysis or Gilbert Syndrome, pharmacologic treatment, viral hepatitis, alcoholic or autoimmune hepatitis, other hepatotoxic drugs. For patients with Gilbert Syndrome, these dose modifications apply to changes in direct bilirubin only. Bilirubin will be fractionated if elevated.	
AST or ALT	
AST or ALT without bilirubin elevation > 2 x ULN	
Same grade as baseline or increase from baseline grade 0 to grade 1 (confirmed 48 – 72 h later)	No dose adjustment required with LFTs monitored per protocol if same grade as baseline or bi-weekly in case of increase from baseline grade 0 to 1
Increase from baseline grade 0 or 1 to grade 2 (> 3.0 – 5.0 x ULN)	
Dose interruption of ribociclib
 
If resolved to ≤ baseline grade in ≤ 21 days, then maintain dose level
 
If resolved to ≤ baseline grade in > 21 days or toxicity recurs, then reduce 1 dose level
 
Repeat liver enzyme and bilirubin tests twice weekly for 2 weeks after dose resumption
 
If toxicity recurs after two dose reductions or recovery to ≤ baseline grade is > 28 days, discontinue ribociclib

Increase from baseline grade 0 or 1 to grade 3 (> 5.0 – 20.0 x ULN)	
Dose interruption of ribociclib until resolved to ≤ baseline grade, then lower 1 dose level of ribociclib
 
Repeat liver enzyme and bilirubin tests twice weekly for 2 weeks after dose resumption
 
If recovery to ≤ baseline grade is > 28 days, discontinue ribociclib
 
If toxicity recurs, discontinue ribociclib

Increase from baseline grade 2 to grade 3 (> 5.0 – 20.0 x ULN)	
Dose interruption of ribociclib until resolved to ≤ baseline grade, then lower 1 dose level of ribociclib
 
Repeat liver enzyme and bilirubin tests twice weekly for 2 weeks after dose resumption

	If toxicity recurs after two dose reductions or recovery to \leq baseline grade is > 28 days, discontinue ribociclib.
Grade 4 ($> 20.0 \times$ ULN)	Discontinue ribociclib
AST or ALT and concurrent Bilirubin	
For patients with normal ALT and AST and total bilirubin at baseline: AST or ALT $> 3.0 \times$ ULN combined with total bilirubin $> 2 \times$ ULN without evidence of cholestasis Or For patient with elevated AST or ALT or total bilirubin at baseline: baseline: [AST or ALT $> 2 \times$ baseline AND $> 3.0 \times$ ULN] OR [AST or ALT $8.0 \times$ ULN]- whichever is lower- combined with [total bilirubin $> 2 \times$ baseline AND $> 2.0 \times$ ULN]	Discontinue ribociclib
Confounding factors and/or alternative causes for increased transaminases should be excluded before dose interruption/reduction. They include but are not limited to: concomitant medications, herbal preparations or dietary supplements, infection, hepato-biliary disorder or obstruction, new or progressive liver metastasis, and alcohol intake.	

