6.6 Study drug discontinuation

Study drug interruption refers to a patient stopping either study drug during the course of the study, but then re-starting it at a later time in the study. If one of the study drugs is discontinued, the other must be discontinued as well. If the study drug ribociclib or letrozole is interrupted for more than 4 weeks, the patient will be permanently discontinued from the study treatment.

All study drug interruptions must be recorded on the appropriate Dosage Administration CRF.

Patients whose ribociclib treatment is interrupted due to an adverse event or abnormal laboratory value must be followed at least once a week for 28 days and subsequently at 28 day intervals, until resolution or stabilization of the event, whichever comes first.

Study drug discontinuation refers to a patient's withdrawal from ribociclib. The reason for discontinuation from treatment must be recorded on the End of treatment CRF.

Patients may be withdrawn from the study treatment if any of the following occur:

- Adverse Event (including, but not limited to QTcF \geq 501 msec, confirmed at repeated ECG measurements and recurrent after dose adjustment was performed; Documented episode of ventricular tachycardia, or ventricular fibrillation; Complete heart block (Grade III AV block) or Second degree AV block Mobitz type II).
- Physician decision
- Progressive Disease
- Protocol deviation
- Study terminated by sponsor
- Adjustments to study treatment that result in discontinuation.
- Use of prohibited medication. Please refer to Section 6.3.3.

Patients who discontinue ribociclib $>$ 28 days should be scheduled for an End of Treatment Visit, whenever possible, after discontinuing ribociclib, at which time all of the assessments listed for the End of Treatment Visit (EoT) will be performed. The complete End of Treatment eCRF documentation should be done within one week. If ribociclib is permanently discontinued, the patient will be considered to have completed study treatment. All patients must have safety evaluations for 30 days after the last dose of study drug. AEs/SAEs with a suspected causality to study treatment must be reported beyond this 30 day safety interval.

Patients who discontinue study treatment should NOT be considered withdrawn from the study. They should return for the assessments indicated in Section 7-1. If they fail to return

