7.2.2.4.1 Hematology

Hematology tests are to be performed according to the Visit Schedules outlined in Table 7-1. For details of the Hematology panel refer to [Table 7-3](#) Hematological tests will be performed at screening, on treatment Day 1 (repeated prior to administration of the study drug, if greater than 7 days prior to Day 1), Cycle 1 Day 15, Cycle 2 Day 1 and 15 and Day 1 of each subsequent cycle and at End of treatment.

In the event of Grade 2, Grade 3 or Grade 4 hematological toxicities that require study drug dose modifications or interruptions, hematological tests should be repeated weekly until recovery to the baseline value or Grade 1.

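### Protocol Table 6-3, WBC grade 3: the recovery threshold for a recurrence (≥1.0 × 10⁹/L) is already met by every grade 3 count; it should be ≥2.0, as for a first event

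*Protocol*

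**What the plan says.** Table 6-3 in Protocol 6.2.1.1 gives the WBC bands as "Grade 2 ($< 3.0 - 2.0 \times 10^9/L" for grade 2, which needs no dose change, and "Grade 3 ($< 2.0 - 1.0 \times 10^9/L" for grade 3. Grade 4 is anything below 1.0 × 10⁹/L.

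For grade 3, one cell covers both the first event and a recurrence. Starting at the first-event threshold it reads "2.0 \times 10^9/L$. Re-initiate ribociclib at the same dose level. If toxicity recurs at grade 3: temporary dose interruption until recovery to $\geq 1.0" (× 10⁹/L). A time rule follows: keep the dose if the recurrence resolves within 7 days, and go down one level if it takes longer.

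The ANC grade 3 row, banded as "Grade 3 ($\geq 0.5 - < 1.0 \times 10^9/L", carries the same recurrence sentence with the same ≥1.0. The platelet grade 3 row says "If toxicity recurs at grade 3: temporary dose interruption until recovery to grade ≤ 1 and reduce ribociclib to the next lower dose level", which repeats the recovery level it sets for a first event.

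On the standing of these tables, 6.2.1.1 says "Clinical judgment of the treating physician should guide the management plan of each patient based on individual benefit/risk assessment". For haematological toxicity that leads to a dose change or interruption, 7.2.2.4.1 says "hematological tests should be repeated weekly until recovery to the baseline value or Grade 1". If ribociclib or letrozole, in the words of 6.6, "is interrupted for more than 4 weeks, the patient will be permanently discontinued from the study treatment".

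**The concern.** A recovery threshold should lie outside the toxicity band that triggered the hold; otherwise there is nothing to recover to. For a recurrent WBC grade 3 event the threshold sits at the bottom of the band. A repeat toxicity is then handled less strictly than the first, and the 7-day rule attached to it has nothing to act on.

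What is at stake is dosing safety and consistency between sites. A site following the text could continue ribociclib at the same dose with WBC still between 1.0 and 2.0. A site that mentally corrects the number would hold the drug and possibly reduce the dose. The exposed group is narrow: recurrent WBC 1.0 to <2.0 with ANC at or above 1.0. Below that ANC, the ANC and febrile neutropenia rows apply in their own right.

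**Working it through.** No figure in the plan has to be reproduced. The check compares each grade band with its recovery threshold (all counts × 10⁹/L, Table 6-3).

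**Band against threshold**

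- WBC grade 3 is [1.0, 2.0). The value 1.0 belongs to grade 3 because grade 4 is <1.0.
- First event: restart at ≥2.0. No value in [1.0, 2.0) qualifies, so the hold works.
- Recurrence: restart at ≥1.0. Every value in [1.0, 2.0) qualifies. Required hold = 0 days, so recovery in more than 7 days is impossible. A count below 1.0 is grade 4 and moves to the next row.
- ANC grade 3 is [0.5, 1.0). No value is ≥1.0, so the identical sentence works there.

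**Rows that give a recovery threshold for a recurrence**

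| Row | First event | Recurrence | Same? |
|---|---|---|---|
| Platelets grade 3 | grade ≤1 | grade ≤1 | yes |
| ANC grade 3 | ≥1.0 | ≥1.0 | yes |
| ANC grade 4 | ≥1.0 | ≥1.0 | yes |
| WBC grade 3 | ≥2.0 | ≥1.0 | **no** |
| WBC grade 4 | ≥1.0 | ≥1.0 | yes |

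Four of five repeat the first-event value. The exception shares its wording with the ANC grade 3 row. The protocol's Amendment 2 summary records that the leukocyte rows were added to this table in the same edit that updated the grade 3 neutropenia text. That fits a carried-over number but does not prove it.

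**Other sections.** The clinical-judgment clause in 6.2.1.1 gives no WBC level. The rule in 7.2.2.4.1 sets how long to repeat counts, not when to restart. No other section supplies a different recurrence threshold.

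**Order of magnitude.** The documents give related grade 3/4 WBC-type events but not recurrences with preserved ANC.

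- Phase Ib study (Protocol 1.2.6), WBC decreased: 3/47 = 6.4%, exact 95% CI 1.3% to 17.5%.
- Reference phase III trial (Table 1-5), WBC decreased: (37 + 2)/334 = 39/334 = 11.7%.
- Same table, leukopenia: (25 + 1)/334 = 26/334 = 7.8%.
- If no patient had both terms: (39 + 26)/334 = 65/334 = 19.5%. With full overlap the figure stays at 11.7%.
- Scaled to 500 patients: 500 × 3/47 ≈ 32; 500 × 39/334 ≈ 58; 500 × 65/334 ≈ 97.

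Table 1-5 prints 1.1% beside the count of 37, but 37/334 = 11.1%; the count is used here. Both sources include only events suspected to be treatment-related, so these are not upper limits. Nor do they estimate the number affected, which is an unknown subset.

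**After correction.** With ≥2.0, no count in [1.0, 2.0) permits restart, and both arms of the 7-day rule can be reached.

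**The case against.** The reading of the cell is hard to dispute, so the case on the other side concerns weight and completeness.

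- **The table is advisory.** A physician could take resolution to mean leaving grade 3, since ≥2.0 appears in the same cell and the 7-day rule makes sense only that way. This limits the harm. It does not repair the text, because that reading sets aside the printed number, and 6.2.1 also says the guidelines need to be applied.
- **The group is small and may no longer exist.** The Amendment 4 summary says enrolment is complete, treatment was planned to end 80 weeks after the last patient started (7.1.3.1), and the SAP is written largely in the past tense. The documents do not show whether anyone was still on ribociclib. This stands as a limit on the practical benefit.
- **WBC grade 4 also restarts at ≥1.0**, which is still inside grade 3. After a one-cell fix, the more severe event would keep the looser restart count. That is a fair point and the row deserves review. Its restart is one dose level lower, however, so it does not license restarting a recurrent grade 3 event at the same dose, and correcting grade 3 does not make it worse.
- **The documents do not state the intended value.** That is true; ≥2.0 is an inference, though it is the only other threshold the cell supplies.
- **The 32, 58 and 97 figures do not size the problem.** Agreed; they are background only.

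**Conclusion.** The concern holds. As printed, the WBC grade 3 recurrence rule requires no hold and makes its own dose-reduction branch unreachable, so a repeat event is handled more leniently than a first one. This follows from the printed bands and thresholds alone.

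The number of patients affected is unknown. The practical weight is moderate: it is a flaw in safety guidance, softened by clinical judgment, by the separate ANC rows and by weekly counts once a dose has been changed or interrupted. It has no bearing on the CBR estimate, the sample size or the SAP. That ≥2.0 was intended is an inference from the first-event threshold in the same cell, the lower edge of grade 2, and the pattern in the other four rows.

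**What to change.** In the recurrence sentence of the WBC grade 3 row, replace ≥1.0 with ≥2.0 × 10⁹/L and keep the 7-day rule. Leave the identical ANC grade 3 sentence alone. With weekly counts the row then works: recovery by day 7, same dose; recovery at a later check up to day 28, one level lower; a hold beyond 4 weeks, permanent discontinuation under 6.6. Review the WBC grade 4 restart level at the same time and state whether restarting within grade 3 at a reduced dose is intended.

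The cost is one number in one cell, by amendment or a short investigator letter if patients are still on treatment. Data collection, sample size and analysis do not change. The one downside is that longer holds may run into the 4-week discontinuation rule, as holds for first events already can.
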